4.3 Excluded or Vulnerable Populations

- Although not the primary source of recruitment, eligible UIC students and employees are welcomed to participate with every effort taken to avoid any semblance of coercion (see section 5.0).
- Eligible volunteers from all racial or ethnic backgrounds are also welcomed to participate.
- Minors and pregnant women will be excluded by virtue of the scientific design. Moreover, the study question is not directed towards minors or pregnant women.

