sonography within 21 days of study start reveals no evidence of follicular development in the face of a negative pregnancy test.

Visits 1 through 5 will occur during the first week of the study protocol. During Visits 1 through 4, subjects will undergo an HCG stimulation test (HCG-ST) in the CRC consisting of a single IM HCG injection during Visit 1 after documenting a negative urine pregnancy test, along with a single blood draw during all 4 visits at 0, 24, 48 and 96 hours after HCG administration to measure serum androgens and 17-hydroxyprogesterone. Visits 1 through 3 will be short lasting ~30 minutes. After one of these short visits, subjects will also undergo a body composition assessment consisting of a whole-body dual-emission X-ray absorptiometry (DEXA) scan in the Integrative Physiology Laboratory (IPL) at [name], and a magnetic resonance image of the abdomen in the Center for Magnetic Resonance Research at [name]. Visit 4 will last ~8 hours during which a cream challenge test (CCT) will also be performed in the CRC consisting of dairy cream ingestion and serial blood draws at 0, 2, 3 and 5 hours after cream ingestion to measure inflammation markers. Visit 5 will last ~7 hours and occur 2 days after the CCT during which subjects will undergo a FS-IVGTT in the CRC to assess insulin sensitivity and glucose-stimulated inflammation.

[figure not shown]
| Table 1. PRE-STUDY SCREENING | | | | |
|--|---------|---|---|---|
| STUDY PROTOCOL | WEEKS → | 0 | 4 | 8 |
| Salicylate Level | | X | X | X |
| Sex Hormone Binding Globulin | | X | | X |
| Body Composition: MRI & DEXA | | X | | |
| HCG Stimulation Test: T, A & 17OHP @ 0, 24, 48 & 96 hours. | | X | | X |
| Cream Challenge Test: MNC-derived ROS, NFκB, RNA & protein inflammat'n markers @ 0, 2, 3 & 5 hours. | | X | | X |
| Frequently Sampled Intravenous Glucose Tolerance Test: glucose, insulin, C-peptide & FFA q 1-30 minutes x 34 samples from -20-240 minutes. | | X | | X |
| Post-Study Safety Tests: CBC & CMP. | | | | X |
| Ovulation Monitoring: BBT from 0-12 weeks; P on 7th day of BBT rise; If P >2 ng/dl documented, vaginal sonography on day of & day after LH surge. | | | | |

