6.1 Subject-Related Procedures

- *Screening* of volunteers to confirm the diagnosis of PCOS will typically be based on previously measured hormone levels. It is anticipated that most subjects with PCOS will be diagnosed by the PI just prior to study entry, and will likely involve performance of a hormonal evaluation within 6 months of beginning the study. However, the timing of previous hormone measurements used to diagnose PCOS will be left to the discretion of the PI. If the relevant tests for this purpose have not been performed previously, the necessary hormone levels will be obtained from a screening blood draw which will also be used to measure a CBC and CMP (maximum 22 ml). Assays to measure prolactin, TSH, LH, FSH, total testosterone, free testosterone, androstenedione, DHEA-S and 17-hydroxyprogesterone (17OHP) along with the CBC and CMP will be performed by the UI Health Clinical Pathology Laboratory. Pregnancy will be ruled out in all subjects immediately prior to study testing before and after treatment with salsalate or placebo using a urine test sensitive enough to detect >50 mIU/L of HCG.
- *Screening* of volunteers with an OGTT to rule out diabetes and to determine IR status will be performed in the CCTS CRC prior to study entry after an overnight fast of ~12 hours. A polyethylene intravenous catheter will be inserted in an arm vein for blood sampling at ~9:00 AM. The size of the catheter (i.e. 18-23-gauge) will be of suitable caliber for the size of the vein used to gain access. A baseline blood sample (9 ml) will be drawn in the fasting state. A 75 gram glucose beverage will subsequently be ingested over 10 minutes. Blood samples (9 ml each) will again be drawn at 30, 60, 90, 120 and 180 minutes following glucose ingestion. Every attempt will be made to insert the intravenous catheter and obtain blood samples on time. However, a sample may be obtained within a fifteen minute window after the scheduled time due to any unforeseen technical difficulty. Upon completion of the test, the indwelling catheter will be removed and subjects will be fed a high carbohydrate snack. Blood glucose and plasma insulin levels will be measured by the UI Health Clinical Pathology Laboratory.

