 - *Dual Energy X-ray Absorptiometry* (DEXA, Model LUNAR iDXA, General Electric Healthcare, Wood Dale, IL) will be performed in the IPL at which time anthropometric measures of height and weight will be taken using standard techniques. These measures are required for the DEXA scan. All female participants will perform a spot pregnancy test prior to DEXA scan. If pregnancy test is positive the participant will be excluded. The instrument emits photons at 2 different energy levels as a detection scanner traverses the body. The detected energy passes through the body with differential attenuation that is computer analyzed to calculate body fat. The total fat quantity, and truncal fat quantity will be measured, the latter of which is defined as the area between the dome of the diaphragm (cephalad limit) and the top of the greater trochanter (caudal limit).³⁷ Fat quantity will also be measured in the central abdominal area (R1 area) which is an area of 50 cm² around the central point of the midline between the lateral iliac crests and the lowest rib margins at the end of normal expiration (the same midline used for waist circumference).³⁸ Study subjects will wear light clothing and lie on their backs during the procedure which takes 10-15 minutes to complete. Subjects will be exposed to a radiation dose of $\leq 0.3 \text{ mrem}$ based upon manufacturer's specifications and calculations from Standford Dosimetry, LLC RADAR Medical Procedure Radiation Dose Calculator. A Radiation Safety Committee review is not required for this amount of research protocol radiation exposure given the estimated effective equivalent dose is below 100 mrem (1 mSv) per year, a limit set by the Nuclear Regulatory Commission for "general public" exposure.

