 - *Magnetic Resonance Imaging* (MRI, Siemens MAGNETOM Trio 3T, Malvern, PA) will be performed at the Center for Magnetic Resonance Research, [name]. The MRI scanner performs an axial scan in the supine position to measure abdominal adiposity as previously described.³⁹ A gradient echo pulse sequence with water suppression to obtain a fat-only image is followed by lipid suppression to obtain a water-only image and no suppression to serve as an anatomic reference. Five 4 mm slices centered at L3 are obtained and the fat signal intensity ratio [$If/(If+Iw)$] is calculated from the fat-only (If) and water-only (Iw) images on a pixel-by-pixel basis to produce a map. The calibration curve obtained from a previous phantom study is used to convert this ratio to a fat percentage value that is used to determine visceral and subcutaneous fat volumes with AnalyzeDirect, Inc. software (Stilwell, KS).³⁹
- *HCG Stimulation Test (HCG-ST):* The test will be performed in the CRC as described by Piltonen et al.⁴⁰ over three (3) short CRC visits. A baseline blood sample (16 ml) will be

[figure not shown]
drawn after an overnight fast of ~12 hours followed by administration of a single intramuscular injection of 5,000 IU HCG (Pregnyl; Schering-Plough, Kenilworth, NJ). Fasting blood samples (16 ml each) will again be drawn at 24, 48, and 96 hours after HCG administration (*please refer to the Risks - Venipuncture / Venous Catheter Blood Sampling subsection of Section 7.0 for the approach and alternatives to venipuncture*). Every attempt will be made to obtain blood samples on time. However, the baseline sample may be obtained within a fifteen minute window and the post-HCG samples may be obtained within a sixty minute window after the scheduled time due to any unforeseen technical difficulty. Gathering of vital signs during the single blood draw visits will be considered if there is any clinical evidence subject instability. Plasma will be isolated from the blood samples collected and stored at -80° C until assayed for testosterone, androstenedione and 17OHP.

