- **Reproductive Risk** – Pregnancy is an exclusion criterion for this study. The risks listed above would apply equally to a developing fetus as well as the primary participant. Potential risks of specific impact to a developing fetus include the small amount of radiation exposure received from the DEXA scan (point 4 above). A negative urine pregnancy test must be documented prior to undergoing the DEXA scan. Salsalate is a Category C drug for pregnancy and use of double barrier contraception will be required during the study unless either the participant or her partner have already undergone permanent sterilization.
- **Loss of confidentiality** is a risk as with all human subject-based medical research owing to disclosure of health information. These disclosures may be mandated by local or national regulatory agencies (i.e. IRB, Food and Drug Administration (FDA)) or may be unintentional. Safeguards regarding both physical and electronic copies of all subject data are in place, as dictated by the current standards of UIC and UI Health.

Except for de-identified research data, all other information relevant to patients collected in the study will be kept confidential, including locked storage of all paperwork, and secure digital storage on a database to which only members of the research group have access. The security and integrity of this database are maintained with the direct assistance and oversight of UI Health Information Technology support teams, and the database is served centrally from a closely monitored, regularly backed up server.

- **Unforeseen Risks** – There may be risks or side effects related to the study that are unknown at this time.

Benefits

- Subjects will receive individual body composition results as well as diabetes risk information from the OGTT. Based on the results of a small pilot study that treated women with PCOS with salsalate, it is possible that subjects receiving salsalate may experience a reduction in circulating androgens and ovulation. However, because individuals respond differently to therapy, it is not known in advance if these potential benefits will occur. There are no anticipated benefits to subjects receiving placebo.

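### The pregnancy test required before the baseline DEXA can be positive because of the study's own HCG injection, and the exclusion rule makes no exception for this

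*Combined protocol and SAP*

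**What the plan says.** Section 6.0 opens the HCG stimulation test with "a single IM HCG injection during Visit 1 after documenting a negative urine pregnancy test". Blood is then drawn at 0, 24, 48 and 96 hours over Visits 1 to 4, and Visits 1 to 3 are the short ones. On the scan it says: "After one of these short visits, subjects will also undergo a body composition assessment". Section 6.1 gives the dose: "administration of a single intramuscular injection of 5,000 IU HCG".

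The DEXA item in Section 6.1 adds a pregnancy check of its own: "All female participants will perform a spot pregnancy test prior to DEXA scan. If pregnancy test is positive the participant will be excluded". Section 7.0 repeats twice, under DEXA scans and under Reproductive Risk, that a negative urine result must be on record before the scan.

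The general pregnancy check is in the screening item of Section 6.1: "Pregnancy will be ruled out in all subjects immediately prior to study testing before and after treatment with salsalate or placebo", by a urine test "sensitive enough to detect >50 mIU/L of HCG". On consequences, Section 4.3 says "Minors and pregnant women will be excluded by virtue of the scientific design" and Section 7.0 says "Pregnancy is an exclusion criterion for this study". Section 6.4 lists DEXA data as descriptive.

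**The concern.** The pregnancy test looks for HCG, and the study injects HCG before every baseline scan. If staff do the spot test when the woman arrives for the scan, a positive may come from the injection, and the DEXA item makes no allowance for that.

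Two things are at stake. First, a woman who is not pregnant could be removed after consent, a screening visit of about four hours, the injection and one to three of the HCG-test draws. Section 11.0 has women who withdraw replaced, so an exclusion handled the same way would mean recruiting another woman. Second, a positive at that point has no clear meaning. Staff could not tell injected HCG from pregnancy, shortly before treatment with a drug that Section 7.0 places in pregnancy Category C.

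**Working it through.** **Order of events.** This is mainly a matter of reading the provisions together.

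| Step | Timing | Source |
|---|---|---|
| Negative urine pregnancy test | Visit 1, before injection | Section 6.0 |
| HCG 5,000 IU | Visit 1 (0 h) | Sections 6.0 and 6.1 |
| DEXA | After Visit 1, 2 or 3: same day, about 24 h or about 48 h after injection | Section 6.0 |
| Spot test; exclusion if positive | Before DEXA, no clock time given | Section 6.1 |

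Every permitted DEXA slot falls after the injection. Section 6.0 lets the order of the main procedures change, but the procedures it names are the HCG test, the cream challenge and the FS-IVGTT. It does not move DEXA ahead of the injection.

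**Can the injected dose reach the test limit?** The plan has no figure of its own to reproduce. The documents give the dose and the limit but no urinary recovery, so the check asks what share of the dose would have to reach the urine.

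Share needed = limit × urine volume / dose. The dose is 5,000 IU = 5,000,000 mIU. Urine output of 1 to 3 L per day is an assumption.

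- Limit as printed, 50 mIU/L, over one day: 50 × 1 to 50 × 3 = 50 to 150 mIU. Divided by 5,000,000, this is 0.001% to 0.003% of the dose.
- Limit of 50 mIU/ml (50,000 mIU/L), assuming that the printed unit is a slip: 50,000 to 150,000 mIU, or 1.0% to 3.0% of the dose.
- Same-day scan 2 to 6 hours after injection (assumed), at 50 mIU/ml, which is 50 IU/L: 50 × 1 × 2/24 = 4.2 IU to 50 × 3 × 6/24 = 37.5 IU, or 0.08% to 0.75% of the dose. At the printed unit these are 1,000 times smaller.

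These are break-even shares, not probabilities. They show that a positive caused by the injection is possible. They do not show how often it would occur.

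**The case against.** The strongest reply is that a compliant reading exists. The DEXA item says only that the test comes before the scan; it does not say after the injection or at the scanner. The negative test at Visit 1, before the injection, would satisfy Section 6.0, the screening item in Section 6.1 and both statements in Section 7.0. On that reading nothing conflicts, and the only gap is that no section makes the link. This stands as a reason to rate the point low, but it does not remove it. The DEXA item describes a spot test of its own, inside a procedure done in a different unit from the one that gives the HCG. Staff who follow it literally could well test at the scan.

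The word excluded is also not defined there. It may mean from the scan only, in which case the loss is one baseline descriptive measure. Sections 4.3 and 7.0 treat pregnancy as a reason to leave the study, so the heavier meaning remains open.

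The safety argument is limited too. On any reading, pregnancy was tested for no more than about 48 hours earlier, and the scan dose is at most 0.3 mrem.

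A reader might infer that the rule would exclude most participants, or use up the recruitment allowance in Section 12.2 (at most 113 patients for 90 completed evaluations). The documents support neither. They give no HCG kinetics from which to derive a frequency. The 20% dropout figure is a ceiling, not an expected rate, and no section says that a woman removed in the first week counts towards the 113.

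**Conclusion.** The point holds as an operational defect in wording. Every baseline DEXA follows the HCG injection, the DEXA item excludes on a positive test, and no section makes an exception for injected HCG. If the spot test is done at the scan, it can wrongly exclude a non-pregnant woman, from the study or at least from the scan, and a positive cannot identify a real pregnancy.

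The conclusion rests on one condition that the documents leave open: that the test is done after the injection. The number of women affected cannot be given.

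A reader might also infer bias in the treatment comparison or a loss of power. The documents do not support that. All women have the same injection and scan at baseline, so exclusion would not depend on arm. DEXA does not enter the primary model in Section 12.3, and the target remains 90 completed evaluations. This is a cheap improvement of minor priority.

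**What to change.** In the DEXA item of Section 6.1, and under DEXA scans and Reproductive Risk in Section 7.0, add two statements:

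- The negative urine pregnancy test documented at Visit 1, before the HCG injection, is the qualifying test for the baseline DEXA.
- A spot test taken between that injection and the baseline DEXA is not used to exclude.

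Alternatively, do the test and the DEXA before the injection. That needs a scanner slot of 10 to 15 minutes before the Visit 1 injection. Leave the pregnancy test before post-treatment testing as it is.

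The first option needs no extra test. Its cost is a qualifying result up to about 48 hours old before a scan of at most 0.3 mrem, plus a minor amendment, which Section 11.0 puts before the DSMB and which presumably also goes to the IRB.

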- **Insulin-Modified FS-IVGTT:** The test will be performed in the CRC two (2) days after the CCT after an overnight fast of ~12 hours as described by Polidori et al.³² An intravenous polyethylene catheter will be inserted in an forearm vein at ~7:10 AM (-50 minutes) for infusing glucose and insulin. Another intravenous catheter will be inserted in a contralateral forearm vein for blood sampling. The size of the catheter (i.e. 18-23-gauge) will be of suitable caliber for the size of the vein used to gain access (*please refer to the Risks - Venipuncture / Venous Catheter Blood Sampling subsection of Section 7.0 for the approach and alternatives to intravenous catheter placement*). Baseline blood samples will be obtained at ~7:40 AM (-20 minutes), ~7:50 AM (-10 minutes), ~7:59 AM (-1 minute) and ~8 AM (0 minutes). The average of the four samples is considered the basal level. A glucose solution (0.3 gm/kg) will be administered intravenously beginning immediately after the 0 minute blood draw. Insulin (20 mU/kg Humulin; Eli Lilly, Indianapolis, IN) delivered in 1 unit/ml infused over 60 seconds starting at ~8:20 AM (20 minutes). Blood samples will be obtained at -20, -10, -1, 0, 1, 2, 3, 4, 5, 6, 7, 8, 10, 12, 14, 16, 19, 22, 23, 24, 25, 27, 30, 40, 50, 60, 70, 80, 90, 100, 120, 150, 180 and 240 minutes. Every attempt will be made to insert the intravenous catheters and obtain blood samples on time. However, all samples with the exception of those used to measure glucose may be obtained within a fifteen minute window after the scheduled time due to any unforeseen technical difficulty. A total of 272 ml of blood (8 ml/sample) will be collected during the entire procedure. All infusions will be stopped at 12 PM. Upon completion of the test, both catheters will be removed, and subjects will be fed a standard lunch. Plasma will be isolated from the blood samples collected and stored at -80° C until assayed for glucose, insulin, C-peptide and FFA. Preparation of glucose and insulin for infusion during the FS-IVGTT procedure will be performed by the UI Hospital Pharmacy Investigational Drug Services.

- *Mathematical Model to Assess Hepatic and Extrahepatic Insulin Clearance.* Hepatic and peripheral insulin clearances were estimated using a model for insulin kinetics during the FS-IVGTT as described in Fig. 3.

The model is based on the following main assumptions:

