1. Endogenously secreted insulin enters the portal circulation where it travels to the liver before reaching the systemic circulation. The insulin secretion rate (ISR) will be calculated by deconvolution using C-peptide kinetic parameters.⁴² The calculated ISR and the known insulin infusion rate will be used as inputs to the model.

2. The rate of delivery of insulin from the systemic circulation to the liver reported in pmoles/minute is equal to the plasma insulin concentration reported in pmoles/liter times the assumed hepatic plasma flow (HPF) rate (0.576 L/min/m²).⁴³
3. Insulin clearance occurs in both the liver and in extrahepatic (peripheral) tissues, which includes kidney, muscle, and adipose tissue. Extrahepatic clearance is assumed to be proportional to the plasma concentration.
4. Hepatic clearance will be modeled using either a linear or a saturable function. Both functions will be tested in each subject, and the one providing the best fit will be retained. Both functions will be considered because some previous studies have suggested linear clearance, whereas others have suggested nonlinear and/or time-dependent clearance.^{30,43-45} No time-dependent changes in parameter values will be modeled.

Given these assumptions, the resulting model requires estimating either three (linear model) or four (saturable) parameters from the measured plasma insulin profiles and calculated ISR.

The following equations and parameters correspond with these main assumptions. The HPF rate used in the equations is the combined plasma flow to the liver from the portal vein and the hepatic artery.

Insulin delivery to liver (pmol/min)

$$\text{Delivery} = \text{ISR} + \text{HPF} \cdot P$$

Hepatic insulin degradation (pmol/min)

$$\text{Linear model} = FE_L \cdot \text{Delivery}$$

$$\text{Saturable model} = \frac{V_{max} \cdot \text{Delivery}}{K_m + \text{Delivery}}$$

$$\text{Extrahepatic insulin degradation (pmol/min)} = CL_P \cdot P$$

P is plasma insulin reported in pmoles/liter, $/SR$ is reported in pmoles/minute, HPF and CL_P are reported in liters/minute, FE_L is hepatic fractional extraction (dimensionless), V_{max} is the maximal hepatic degradation rate reported in pmoles/minute, and K_m is the hepatic insulin delivery rate at which 50% of maximal degradation occurs reported in pmoles/minute.

The differential equations for the linear (Equation 1) and saturable (Equation 2) assumptions are as follows:

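### The 15-minute lateness window for FS-IVGTT samples is longer than every sampling gap before 100 minutes, and its glucose exception conflicts with draws shared by all analytes

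*Combined protocol and SAP*

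**What the plan says.** The insulin-modified FS-IVGTT is described in Section 6.1. The early schedule reads "Blood samples will be obtained at -20, -10, -1, 0, 1, 2, 3, 4, 5, 6, 7, 8, 10, 12, 14" and continues "16, 19, 22, 23, 24, 25, 27, 30, 40, 50, 60", then runs at 10-minute steps to 100 minutes and at wider steps to 240 minutes. Insulin is infused over one minute from minute 20, so the 22-minute draw is the first after it.

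The staff are to try to keep to time. If an unexpected technical problem arises, however, "all samples with the exception of those used to measure glucose may be obtained within a fifteen minute window after the scheduled time".

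On volume, the same paragraph says: "A total of 272 ml of blood (8 ml/sample) will be collected during the entire procedure". The overview table in Section 6.0 lists the analytes together: "glucose, insulin, C-peptide & FFA q 1-30 minutes x 34 samples from -20-240 minutes".

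The model description in Section 6.1 derives the insulin secretion rate (ISR) from C-peptide by deconvolution and states: "The calculated ISR and the known insulin infusion rate will be used as inputs to the model". Three or four clearance parameters are then fitted to the measured insulin profile, and S_I comes from MINMOD. Section 12.2 names S_I as the secondary outcome of Aim 1, and Section 12.1 defines it as adjusted for insulin clearance.

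The text does not say whether actual draw times are recorded or entered in these fits, or what happens to a sample drawn after a later scheduled one.

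**The concern.** A lateness allowance is harmless when it is short relative to the spacing of the samples. The protocol's other uses of 15 minutes meet that test: OGTT draws are at least 30 minutes apart and cream challenge draws at least 60. The FS-IVGTT schedule does not, because its early draws are minutes apart around a glucose bolus and then an insulin infusion.

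The analytes left free to float are the ones on which the method depends. Section 2.0 says that salsalate lowers hepatic insulin clearance, that this confounds clamp studies, and that the model-based FS-IVGTT analysis was chosen to deal with it. That analysis needs a well-timed insulin curve and a well-timed C-peptide curve. What is at stake is the precision of S_I and the credibility of the secretion and clearance estimates. The primary outcome, HCG-stimulated testosterone AUC, is not touched.

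**Working it through.** **1. The plan's own volume.** The list has 4 times up to and including 0, 8 from 1 to 8, 4 from 10 to 16, 2 at 19 and 22, 5 from 23 to 30, 7 from 40 to 100, and 4 at 120, 150, 180 and 240. That makes 4 + 8 + 4 + 2 + 5 + 7 + 4 = 34, and 34 × 8 ml = 272 ml, the stated total. No blood is budgeted for separate glucose draws.

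**2. Two readings of the exception.**
- Taken literally, every draw is used to measure glucose, so the exception covers all 34 and the window covers none.
- Taken as apparently meant, glucose is held to time while insulin and C-peptide from the same scheduled point may be up to 15 minutes later. One 8 ml draw cannot satisfy both.

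**3. Window against gaps.** There are 33 gaps.
- Of these, 29 are under 15 minutes, and they are all the gaps before 100 minutes. The last four are 20, 30, 30 and 60 minutes.
- All 19 gaps from 0 to 30 minutes are 1, 2 or 3 minutes.
- The window of the 1-minute draw reaches 11 later scheduled draws (2 to 8, 10, 12, 14, 16). That of the 3-minute draw, which ends at 18, reaches 9 (4 to 8, 10, 12, 14, 16). That of the 22-minute draw, which ends at 37, reaches 5 (23, 24, 25, 27, 30).

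**4. What a late insulin draw does to one subject's estimates.** This is a noise-free illustration using the protocol's linear clearance model (Equation 1), its hepatic plasma flow of 0.576 L/min/m², and the standard glucose minimal model. Glucose is kept on time and ISR is held at its true value. The kinetics are assumed: FE_L 0.4 to 0.7, CL_P 0.3 to 0.8 L/min, V_P 4 to 7 L, body weight 60 to 100 kg. With half-life = ln 2 × V_P / (HPF × FE_L + CL_P), the insulin half-life is 1.9 to 4.7 minutes. With all draws on time, the refit returns the true clearance and S_I within about 1%.

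In the central case (FE_L 0.55, CL_P 0.5, V_P 4, half-life 2.7 minutes), insulin is about 1349 pmol/L at 22 minutes, 457 at 27 and 133 at 37. A 22-minute sample drawn at 37 therefore records 133 / 1349, about 10% of the right value. The true CL_IV is about ln 2 × 4 / 2.7 = 1.03 L/min. The refit at nominal times gives FE_L 0 and CL_P 2.39, so CL_IV is 2.39, about 2.3 times the truth (+134% before rounding).

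| Late draws | S_I, nominal times | CL_IV, nominal times | S_I, actual times |
|---|---|---|---|
| 22 min only, 15 min late | +10% to +44% | +69% to +251% | +5% to +19% |
| 22–27 min, 2 min late | +9% to +62% | +28% to +108% | +7% to +40% |
| 22–27 min, 5 min late | +21% to +166% | +72% to +301% | +22% to +142% |
| 1–8 min, 5 or 15 min late (central case) | 0% to −4% | −6% to −7% | 0% to −2% |

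With actual times the clearance fit recovers (CL_IV 0%). S_I does not fully recover, because the insulin peak was never sampled. The sign for S_I is not fixed either: with every draw after time 0 late by 2 or 5 minutes in the central case, the shift is −6% or +8% at nominal times and −12% or −7% at actual times.

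**5. Spread across subjects if lateness is random.** A second simulation assumed a true S_I of 4.0, delays uniform on 0 to 15 minutes, glucose CV 1.5%, nominal times and 40 tests per setting. The SD of the estimate was 0.15 with no late samples, and 0.32, 0.40 and 0.55 with 10%, 25% and 50% late. Mean shifts were about +2%, +4% and +8%. The first is 0.08 with standard error 0.32 / √40 = 0.05, so it cannot be told from zero. With actual times the SD was 0.20 to 0.25.

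Section 12.2 gives SDs of 2.7 and 1.8 before and after treatment in another insulin-resistant population. If the units are comparable, √(2.7² + 0.55²) = 2.76 and √(1.8² + 0.55²) = 1.88, an inflation of 2% to 5%. With 0.32 it is about 1% to 2%.

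**The case against.** Four arguments carry weight.

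- **The literal text may already protect insulin.** If every draw is a glucose sample, none may be late, and the defect is redundant wording. That is one of two readings. The other, in which the window does something, is the one that staff looking for an allowance would be likely to apply. The sentence needs correcting on either.
- **The allowance is for contingencies.** It applies only to an unexpected technical problem, after an effort to keep to time. A reader might infer routine lateness; the documents do not say that, and the 10% to 50% rates above have no basis in them. This stands.
- **Silence is not evidence of nominal times.** A reader might infer that scheduled times will be used. The documents do not say so, and the blood sampling plan and laboratory flow charts are appendices that are not in the reviewed text. This stands for the clearance figures, which depend on nominal times. It only partly answers the S_I figures, because a missed peak is lost even when times are exact.
- **Error in S_I is not bias in the trial.** The trial is randomised and double-blind, and Section 12.3 adjusts for the pre-treatment value. Lateness from technical problems should not depend on arm, so its main effect is noise. This stands. The one caveat is that the size of the error depends on clearance, which Section 2.0 expects salsalate to change. Complete cancellation is therefore not assured, but the documents give no basis for putting a size on any remainder.

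**Conclusion.** The point holds in a limited form. What follows from the documents alone is that a 15-minute window sits over gaps of 10 minutes or less for every draw before 100 minutes, and that the glucose exception cannot be squared with one 8 ml draw serving four analytes. These passages must be reconciled.

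If the allowance is used, it adds error to S_I and to the secretion and clearance estimates. The damage is concentrated in the draws at 22 to 27 minutes; delays confined to 1 to 8 minutes matter little. The percentages rest on assumed kinetics, on which draws are late, on assumed late rates and, for clearance, on nominal times being used. Averaged over subjects under the random-delay assumptions, the SD of S_I grows by only about 1% to 5%.

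A reader might go further and conclude that S_I is invalid or that the salsalate versus placebo comparison is biased. Neither is shown: no frequency of late draws is given, and nothing ties lateness to treatment. The point is worth correcting because S_I is a named secondary outcome and the remedy is nearly free.

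**What to change.** 1. Delete the 15-minute window for FS-IVGTT draws, or keep it only from 100 minutes on, where the gaps are 20 minutes or more. A cut-off at 60 minutes would not do, because the gaps from 60 to 100 are 10 minutes.
2. Remove the glucose exception, or state how it works when one draw serves all four analytes.
3. Record the clock time of every draw.
4. State that actual times enter MINMOD, the C-peptide deconvolution and the clearance model. This complements the first change and does not replace it, since actual times cannot restore an unsampled insulin peak.

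The cost is a short wording change, one recorded time per tube, and an occasional late draw logged as a deviation.
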